1 SYNOPSIS

Title: A Phase 3, Multicenter, Double-masked, Randomized, Vehicle-controlled, Parallel-group Study Evaluating the Safety and Efficacy of BID Dosing of AGN-190584 in Subjects with Presbyopia	
Background and Rationale:	This study evaluates pilocarpine HCl 1.25% (AGN-190584) as a noninvasive, reversible, pharmacological treatment for presbyopia. The purpose of this study is to evaluate AGN-190584 when administered twice daily.
Objective(s) and Endpoint(s):	
The objective of this study is to evaluate the safety and efficacy of AGN-190584 when administered bilaterally, twice daily for 14 days in subjects with presbyopia.
 
The primary efficacy endpoint is the proportion of subjects gaining 3 lines or more in mesopic, high-contrast, binocular DCNVA with no more than 5-letter loss in mesopic CDVA with the same refractive correction at Day 14, Hour 9 (3 hours after the second dose).
 
The key secondary endpoint is the proportion of subjects gaining 3 lines or more in photopic, high-contrast, binocular DCNVA with no more than 5-letter loss in photopic CDVA with the same refractive correction at Day 14, Hour 9 (3 hours after the second dose).
 
Additional secondary endpoints are the proportion of subjects gaining 2 lines or more in mesopic, high-contrast, binocular DCNVA with no more than 5-letter loss in mesopic CDVA with the same refractive correction at Day 14, Hour 9 (3 hours after the second dose); and the proportion of subjects achieving 20/40 or better in mesopic, high-contrast, binocular DCNVA with no more than 5-letter loss in mesopic CDVA with the same refractive correction at Day 14, Hour 9 (3 hours after the second dose).
 
Plasma concentrations of AGN-190584 will be assessed at selected sites in approximately 10% of all enrolled subjects.
 
Safety will be assessed based on adverse events, vital signs, mesopic and photopic high-contrast binocular CDVA, intraocular pressure, slit-lamp biomicroscopy, manifest refraction, dilated fundoscopic examination, postdose tolerability (for subjects reporting specific ocular symptoms), drop comfort, and pregnancy test.

Investigator(s):	Multicenter
Study Site(s):	Approximately 20 sites in the United States
Study Population and Number of Subjects to be Enrolled:	Approximately 200 male and female subjects with objective and subjective evidence of presbyopia
Investigational Plan:	This is a Phase 3, multicenter, 14-day, double-masked, randomized, vehicle-controlled, parallel-group study evaluating the safety and efficacy of BID bilateral dosing with AGN-190584 in subjects with presbyopia.
Key Eligibility Criteria:	Adult subjects 40 to 55 years of age with objective and subjective evidence of presbyopia

Study Drug and Duration of Treatment:	Eligible subjects will be randomized in a 1:1 ratio to receive either AGN-190584 or vehicle dosed twice daily, in each eye, for 14 days.
Date of Protocol Synopsis:	21 October 2021

2 INTRODUCTION

2.1 Background and Rationale

Why Is This Study Being Conducted?

The decline of near vision is common among older adults. In 2005, 1.044 billion people globally were estimated to have presbyopia, and prevalence is expected to increase to 1.782 billion by 2050.¹ Both nonsurgical and surgical methods for the correction of presbyopia are available. Traditional nonsurgical methods of refractive correction for presbyopia include the use of dedicated reading spectacles, bifocal or varifocal spectacles, and monovision or multifocal contact lenses. A number of surgical techniques are also used for the treatment of presbyopia, which include monovision photorefractive keratectomy (PRK) or laser-assisted in situ keratomileusis (LASIK), conductive keratoplasty, intraocular lenses, and corneal inlays. However, for each of the existing technologies mentioned above, visual quality is reduced at 1 or more viewing distances (near, intermediate, or distance), and each comes with its own unique safety risks and associated complications. For example, bifocals and progressive lenses (e.g., reading glasses, contacts) produce optical aberrations and can increase the risk of falls.^{2,3} Multifocal optics reduce image quality uniformly at all viewing distances. For surgical technologies, surgical risks, the need for repositioning and explantation, and/or regression of effect have limited their widespread adoption.⁴⁻⁶ Thus, there remains a need for a noninvasive, reversible, pharmacological treatment for presbyopia.

Pilocarpine is a muscarinic receptor agonist that mimics the actions of the parasympathetic neurotransmitter, acetylcholine, on smooth muscle. This causes 2 effects that enhance near vision: 1) contraction of the iris sphincter muscle, resulting in pupil constriction (miosis); reducing the pupil size has long been recognized as an effective way to increase the useful depth of focus, in part by reducing peripheral aberrations⁷, and 2) contraction of the ciliary muscle, resulting in central lens steepening and lens accommodation (focusing from distance to near).⁸

Pilocarpine ophthalmic solutions are currently used for the reduction of elevated intraocular pressure (IOP) in patients with open-angle glaucoma or ocular hypertension, management of acute angle-closure glaucoma, prevention of postoperative elevated IOP associated with laser surgery, and induction of miosis.⁹ Currently the use of pilocarpine ophthalmic solution is limited by the commonly experienced adverse event (AE) of temporal and periorbital headache (i.e., brow ache), which is believed to be due to the rapidity of the ciliary muscle contraction.¹⁰ However, AbbVie (formerly Allergan) has established an acceptable safety profile of AGN-190584 in 3 Phase 2 clinical studies (Studies 199201-007, 199201-009, and 199201-010) and 2 Phase 3 studies (1883-301-013 and 1883-302-013). This is likely because the posology of pilocarpine evaluated for the treatment of presbyopia to date is of lower concentration (0.5% to 1.5%) and less frequently administered (once to twice daily) than for the treatment of glaucoma (1.0% to 4.0% administered up to 4 times daily). As a result, discontinuation rates for all clinical studies were generally low and safety parameters were not clinically significant between subjects who received AGN-190584 compared to subjects who received vehicle or a combination therapy. The majority of AEs reported in any treatment group were mild to moderate in severity. More detailed information regarding clinical safety findings, clinical efficacy findings, chemistry, and pharmacology is provided in the Investigator's Brochure (IB).

2.2 Benefits and Risks to Subjects

Currently available approaches to presbyopia correction include nonsurgical options (spectacles or contact lenses) and surgical options (PRK or LASIK, conductive keratoplasty, intraocular lenses, or corneal inlays). Each approach has its own risk-benefit ratio. Because the risk-benefit ratio with nonsurgical options is generally lower than that of surgical procedures, both historical and contemporary practice has been to attempt nonsurgical or pharmacological treatment before resorting to more invasive alternatives. Although the use of spectacles and contact lenses to correct presbyopia is widespread, this approach has limitations.

Multifocal spectacles impair depth perception and edge-contrast sensitivity at critical distances for detecting obstacles in the environment³, and multifocal lenses have a corridor of nondistorted vision. For these reasons, older people are more than twice as likely to fall when wearing multifocal spectacles, and many subjects have difficulty adjusting to using them.^{2,3} As a result, AbbVie is developing a noninvasive, reversible, pharmacological treatment for presbyopia.

More detailed information about the known and expected benefits and risks and reasonably expected AEs of AGN-190584 may be found in the IB.

Considering the Coronavirus Disease - 2019 (COVID-19) pandemic, the benefits and risks to subjects participating in this study have been evaluated. Based on the limited information to date, no additional risk to study subjects is anticipated with the use of AGN-190584; however, the risk of study activity participation should be evaluated by the investigator.

3 OBJECTIVES AND ENDPOINTS

3.1 Objectives, Hypotheses, and Estimands

Objectives

The primary objective of this study is to evaluate the safety, efficacy, and pharmacokinetics of AGN-190584 when administered bilaterally, twice daily for 14 days in subjects with presbyopia.

Hypotheses

The clinical hypotheses are that AGN-190584 ophthalmic solution dosed bilaterally, twice daily (Hour 0 and Hour 6) for 14 days will demonstrate a significant improvement in distance-corrected near visual acuity (DCNVA) over vehicle after the second dose, and AGN-190584 ophthalmic solution dosed bilaterally, twice daily for 14 days will demonstrate an acceptable safety and tolerability profile.

Table 1. Hypotheses for the Primary and the Key Secondary Efficacy Endpoints

Hypothesis	Efficacy Endpoints
H1	Primary: The proportion of subjects gaining 3 lines or more in mesopic, high-contrast, binocular DCNVA with no more than 5-letter loss in mesopic CDVA with the same refractive correction at Day 14, Hour 9 (3 hours after the second dose)
H2	Key Secondary: The proportion of subjects gaining 3 lines or more in photopic, high-contrast, binocular DCNVA with no more than 5-letter loss in photopic CDVA with the same refractive correction at Day 14, Hour 9 (3 hours after the second dose)

DCNVA = distance-corrected near visual acuity; CDVA = corrected distance visual acuity

Estimands

Estimand attributes are described in [Table 2](#).

Table 2. Summary of the Estimand Attributes of the Primary and the Key Secondary Efficacy Endpoints

Estimand Label	Attributes of the Estimand				
	Treatment	Endpoint	Population	Handling of Intercurrent Events	Statistical Summary
Estimand for the primary endpoint	AGN-190584 or vehicle	The proportion of subjects gaining 3 lines or more in mesopic, high-contrast, binocular DCNVA with no more than 5-letter loss in mesopic CDVA with the same refractive correction at Day 14, Hour 9 (3 hours after the second dose)	ITT	The composite strategy will be applied to handle the intercurrent events. Missing data will be regarded as a nonresponder for the primary endpoint.	The difference and the corresponding 95% confidence interval in the proportion of subjects gaining 3 lines or more in mesopic, high-contrast, binocular DCNVA with no more than 5-letter loss in mesopic CDVA with the same refractive correction at Day 14, Hour 9 between AGN-190584 and vehicle.
Estimand for the key secondary endpoint	AGN-190584 or vehicle	The proportion of subjects gaining 3 lines or more in photopic, high-contrast, binocular DCNVA with no more than 5-letter loss in photopic CDVA with the same refractive correction at Day 14, Hour 9 (3 hours after the second dose)	ITT	The composite strategy will be applied to handle the intercurrent events. Missing data will be regarded as a nonresponder for the key secondary endpoint.	The difference and the corresponding 95% confidence interval in the proportion of subjects gaining 3 lines or more in photopic, high-contrast, binocular DCNVA with no more than 5-letter loss in photopic CDVA with the same refractive correction at Day 14, Hour 9 between AGN-190584 and vehicle.

DCNVA = distance-corrected near visual acuity; CDVA = corrected distance visual acuity; ITT = intent to treat

3.2 Primary Endpoint

The primary endpoint is the proportion of subjects gaining 3 lines or more in mesopic, high-contrast, binocular DCNVA with no more than 5-letter loss in mesopic CDVA with the same refractive correction at Day 14, Hour 9 (3 hours after the second dose).

3.3 Secondary Endpoints

Key Secondary Endpoint

1. Proportion of subjects gaining 3 lines or more in photopic, high-contrast, binocular DCNVA with no more than 5-letter loss in photopic CDVA with the same refractive correction at Day 14, Hour 9 (3 hours after the second dose)

Supportive Secondary Endpoints

1. Proportion of subjects gaining 2 lines or more in mesopic, high-contrast, binocular DCNVA with no more than 5-letter loss in mesopic CDVA with the same refractive correction at Day 14, Hour 9 (3 hours after the second dose)
2. Proportion of subjects achieving 20/40 or better in mesopic, high-contrast, binocular DCNVA with no more than 5-letter loss in mesopic CDVA with the same refractive correction at Day 14, Hour 9 (3 hours after the second dose)

3.4 Additional Efficacy Endpoints

1. Change from baseline in mesopic Near Vision Presbyopia Task-based Questionnaire (NVPTQ) Performance score at Day 14, Hour 9 (3 hours after the second dose)
2. Change from baseline in Presbyopia Impact and Coping Questionnaire (PICQ) Coping score at Day 14, Hour 3
3. Change from baseline in Visual Function Assessment application (VFA app) at Day 14, Hour 9 (3 hours after the second dose)
 - Change from baseline in average number of blinks per minute
 - Change from baseline in median working distance (centimeters)
 - Change from baseline in median magnification level (%) from the original size
 - Change from baseline in reading speed (words per minute)
 - Change from baseline in median contrast level (%) based on the original value

3.5 Pharmacokinetic Endpoints

Blood samples for the quantitation of AGN-190584 in subject's plasma will be collected from approximately 10% of enrolled subjects at selected sites.

3.6 Safety Endpoints

The safety measurements will include AE, vital signs (blood pressure and heart rate), mesopic and photopic, high-contrast, binocular CDVA, IOP, slit-lamp biomicroscopy, manifest refraction, dilated fundoscopic examination, postdose tolerability assessment, drop comfort questionnaire, and pregnancy test.

3.7 Patient Reported Outcomes

Patient-reported outcome (PRO) questionnaires are administered in this study. The **VFA app** should be administered as well.

At screening, subjects will answer questions on vision functioning and health-related quality of life using the **NEI VFQ-25**, including the near vision subscale items (Questions A3 to A5) from the Appendix of Optional Additional Questions.

Subjects will also complete the Ocular Surface Disease Index (**OSDI**) at screening, which assesses symptoms of ocular irritation and their impact on vision-related functioning.

Each subject will also perform 4 paper-based near vision reading tasks under mesopic conditions. Subjects will subsequently rate their vision-related reading ability and satisfaction with their vision-related reading ability by completing the **NVPTQ**.

Subjects will also answer questions assessing the impact of presbyopia on their life and need for compensatory coping mechanisms using the **PICQ**.

Subjects will also answer single-item questions on their overall global impression of status (**PGIS**) and their overall global impression of change (**PGIC**).

After study drug administration, subjects will complete the **Drop Comfort Questionnaire** to evaluate comfort of the study drug after administration.

Finally, the **VFA app** will be used to assess the subject's ability to read on electronic devices.

For questionnaires completed on an electronic platform, if technical issues prevent the questionnaire from being completed, responses can be written down on source documents (preferably a paper copy of the questionnaire if available) and entered when the electronic platform is available.

4 INVESTIGATIONAL PLAN

[figure not shown]
4.1 Overall Study Design and Plan

This is a Phase 3, multicenter, double-masked, parallel-group, vehicle-controlled study in subjects with presbyopia. Subjects will receive AGN-190584 or vehicle dosed twice daily, bilaterally, for 14 days. Approximately 200 subjects with presbyopia will be enrolled at approximately 20 sites in the United States.

The study consists of the following visits: screening (Days -30 to -1), Day 1 (baseline), Day 7 (\pm 2 days), and Day 14 (\pm 2 days). A study schema is shown in [Figure 1](#). Subjects will receive either AGN-190584 or vehicle dosed twice daily, bilaterally, for 14 days beginning on Day 1. On nonvisit days, subjects will be instructed to instill one drop of the dispensed study drug in each eye twice daily, with each dose administered 6 hours apart. On visit days, study drug will be instilled bilaterally by designated site personnel at Hour 0 (8 AM \pm 1 hour) and Hour 6 (time measured 6 hours from the time of completion of the Hour 0 study drug administration). Study procedures on visit days are provided in the Activity Schedule ([Appendix D](#)) and further guidance regarding study procedures are located in the Operations Manual ([Appendix F](#)).

Adult subjects 40 to 55 years of age with objective and subjective evidence of presbyopia will be enrolled. See Section [5](#) for information regarding eligibility criteria.

Figure 1. **Study Schema**

At selected sites, blood will be collected for pharmacokinetic (PK) on Days 1 and 14 at Hours 0, 0.25, 0.5, 1, 3, 6 [pre-dose], 6.25, 6.5, 7, 9, 12

4.2 Discussion of Study Design

Choice of Control Group

A vehicle control group is a recognized comparative evaluator of safety and efficacy in clinical trials.

Appropriateness of Measurements

Standard statistical, PK, and clinical procedures will be used in this study. All efficacy and safety-related measurements in this study are commonly used for assessing presbyopia. All clinical procedures in this study are standard and generally accepted.

Suitability of Subject Population

The study population will include male and female adults 40 to 55 years of age with objective and subjective evidence of presbyopia. Subjects with any evidence of ocular conditions that could affect the safety of the subject or interpretation of efficacy parameters will not be enrolled.

Selection of Doses in the Study

The dose selection in this study is based on modeling and the analysis of safety and efficacy data from Phase 2 Studies 1991201-007, 199201-009, 199201-010 and Phase 3 Studies 1883-301-013 and 1883-302-013. AGN-190584 (pilocarpine hydrochloride) 1.25% is expected to be efficacious with an acceptable safety profile.

5 STUDY ACTIVITIES

5.1 Eligibility Criteria

Subjects must meet all of the following criteria in order to be included in the study. Anything other than a positive response to the questions below will result in exclusion from study participation.

Consent

- 1. Subjects must voluntarily sign and date an informed consent, approved by an independent ethics committee (IEC)/institutional review board (IRB), prior to the initiation of any screening or study-specific procedures.

Demographic and Laboratory Assessments

- 2. Adult male or female, 40 to 55 years of age inclusive at the time of the screening visit
- 3. Are willing and able to comply with procedures required in this protocol.

Disease/Condition Activity

- 4. Subject meets the following ocular conditions:
 - Subjective complaints of poor near vision that impact activities of daily living, as defined by at least a moderate impact (score ≥ 3) on at least 1 question on the NEI VFQ-25 Questions 5 to 7 in the main questionnaire or Near Vision Subscale, Questions A3 to A5 in the Appendix of Optional Additional Questions, at the screening visit
 - Best cycloplegic distance correction at screening in the range of spherical -4.00 D to +1.00 D inclusively and cylinder $\leq \pm 2.00$ D with photopic, high-contrast binocular CDVA of 20/25 or better at the screening and baseline visits

- Photopic, high-contrast binocular CDVA of 20/32 or better by habitual monofocal correction (either spectacles or contact lenses), or willing to wear new monofocal correction spectacles to achieve photopic, high-contrast CDVA of 20/32 or better during the study
- Mesopic, high-contrast binocular DCNVA of 20/40 (J3) to 20/100 (J10) at the screening and baseline visits
- Photopic, high-contrast, near visual acuity correctable to 20/40 (J3+) or better in each eye at the screening visit
- Mesopic pupil diameter < 8.0 mm in both eyes at the screening visit

✓ 5. Subject does not meet any of the following ocular conditions:

- Severe dry eye disease (defined as total corneal staining \geq grade 3 on the 5-point Oxford scale and an OSDI score of > 33) at the screening visit
- Corneal abnormalities (including keratoconus, corneal scar, Fuchs' endothelial dystrophy, guttata, or edema) in either eye that are likely to interfere with visual acuity
- Narrow iridocorneal angles (Shaffer grade ≤ 2 or lower on gonioscopy examination), history of angle-closure glaucoma, or previous iridotomy
- History of iris trauma, Adie's tonic pupil, abnormal pupil shape in either eye, or anisocoria > 1 mm between pupils under mesopic conditions at the screening visit
- Lens opacity in either eye that is determined to cause significant disturbance of the central visual axis on screening biomicroscopy
- Diagnosis of any type of glaucoma or ocular hypertension
- Bifocal or multifocal spectacles or contact lenses for habitual correction. Subjects willing to wear study-provided monofocal correction (either spectacles or contact lenses) during the study can be enrolled.
- Had cataract surgery, phakic intraocular lens surgery, corneal inlay surgery, radial keratotomy, or any intraocular surgery. However, subjects with history of PRK or LASIK with CDVA meeting inclusion criteria will be allowed to enroll.
- Presence of any ocular condition that, in the opinion of the investigator, could affect the safety of the subject or interpretation of efficacy parameters (e.g., uveitis, retinal detachment)
- Concurrent use of temporary or permanent punctal plugs or history of punctal cautery in one or both eyes

Subject History

✓ 6. No history of the following:

- Uncontrolled systemic disease
- Any clinical condition or previous surgery that might affect the absorption, distribution, biotransformation, or excretion of AGN-190584

- A condition or a situation that, in the investigator's opinion, may put the subject at significant risk, may confound the study results, or may interfere significantly with the subject's participation in the study
- Abnormal or clinically significant results according to the investigator or designee, on physical/ophthalmic examination or medical history
- clinically significant (per investigator's judgment) drug or alcohol abuse within the last 6 months
- clinically significant medical conditions/disease state or any other reason that the investigator determines would interfere with the subject's participation in this study or would make the subject an unsuitable candidate to receive the study drug
- allergic reaction or significant sensitivity to constituents of the study drug (and its excipients) and/or other products in the same class (cholinergic agonist)

✓ 7. No known active severe acute respiratory syndrome coronavirus 2 (SARS-CoV-2) infection. If a subject has signs/symptoms suggestive of SARS-CoV-2 infection, the subject must have a negative molecular (e.g., polymerase chain reaction [PCR]) test result. Subjects who do not meet SARS-CoV-2 infection eligibility criteria must be screen failed, and may only rescreen after they meet the following SARS-CoV-2 infection viral clearance criterion:

✓ 8. At least 14 days since the first PCR test result have elapsed in an asymptomatic subject or 14 days since recovery, defined as resolution of fever without use of antipyretics and improvement in symptoms

Contraception

- ✓ 9. For all females of childbearing potential; a negative urine pregnancy test at the screening visit and at baseline prior to the first dose of study drug
- ✓ 10. Female subjects of childbearing potential must practice at least 1 protocol-specified method of birth control, that is effective from Study Day 1 through study exit. Female subjects of nonchildbearing potential do not need to use birth control.
- ✓ 11. Female who is not pregnant or breastfeeding, and is not considering becoming pregnant or donating eggs during the study or for approximately 30 days after the last dose of study drug.

Concomitant Medications

- ✓ 12. Subject must not use any medications that may have a substantial effect on visual function or the optical properties of the eye (defined in Section 5.3) at least 2 weeks prior to the first dose of study drug, Day 1.
- ✓ 13. Subject must not use any ocular medications other than the study drug or medications administered to conduct study procedures at the screening and Day1 (baseline) visit
- ✓ 14. Subject must not have been treated with any investigational drug within 30 days or 5 half-lives of the drug (whichever is longer) prior to the first dose of study drug, be currently enrolled in another clinical study, or have been previously enrolled in this study.

- 15. Subject must not have enrolled in the Phase 3 AGN-190584 Studies 1883-301-013 or 1883-302-013.

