5.2 Contraception Recommendations

Contraception Requirements for Females

Subjects must follow the following contraceptive guidelines as specified:

- Females, Nonchildbearing Potential

Females do not need to use birth control during or following study drug treatment if considered of nonchildbearing potential due to meeting any of the following criteria:

1. Premenopausal female with permanent sterility or permanent infertility due to one of the following:
 - Permanent sterility due to a hysterectomy, bilateral salpingectomy, bilateral oophorectomy
 - Nonsurgical permanent infertility due to Mullerian agenesis, androgen insensitivity, or gonadal dysgenesis; investigator discretion should be applied to determining study entry for these individuals.
2. Postmenopausal female
 - Age \leq 55 years with no menses for 12 or more months without an alternative medical cause

- Females, of Childbearing Potential
 - Females of childbearing potential must avoid pregnancy while taking study drug(s) and for at least 30 days after the last dose of study drug.
 - Females must commit to one of the following methods of birth control:
 - Combined (estrogen and progestogen containing) hormonal birth control (oral, intravaginal, transdermal, injectable) associated with inhibition of ovulation-initiated at least 30 days prior to study Baseline Day 1
 - Progestogen-only hormonal birth control (oral, injectable, implantable) associated with inhibition of ovulation initiated at least 30 days prior to study Baseline Day 1
 - Bilateral tubal occlusion/ligation (can be via hysteroscopy, provided a hysterosalpingogram confirms success of the procedure)
 - Intrauterine device
 - Intrauterine hormone-releasing system
 - Vasectomized partner (provided the partner has received medical confirmation of the surgical success of the vasectomy and is the sole sexual partner of the trial subject)
 - Practice true abstinence, defined as: refraining from heterosexual intercourse when this is in line with the preferred and usual lifestyle of the subject (periodic abstinence)

[e.g., calendar, ovulation, symptothermal, post-ovulation methods] and withdrawal are not acceptable)

- Progestogen-only oral hormonal contraception, where inhibition of ovulation is not the primary mode of action, initiated at least 30 days prior to Study Day 1
- Male or female condom with or without spermicide
- Cap, diaphragm, or sponge with spermicide

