3.8 Clinical Laboratory Tests

Pregnancy Tests (Urine)

Pregnancy testing should not be performed for postmenopausal women.

A urine pregnancy test will be performed at screening, Day 1, and Day 14 (or upon confinement in each period) for all female subjects of childbearing potential. More frequent pregnancy tests can be performed throughout the study at the investigator's discretion or if required per local/country requirements.

If the baseline urine pregnancy test is negative, then dosing with study drug may begin.

If the baseline or post-baseline urine pregnancy test is positive, dosing with study drug must be withheld and a serum pregnancy test is required.

Unless a woman is suspected to have become pregnant, additional pregnancy testing during the clinical trial is not necessary.

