7.4 Visual Acuity Charts Used for Each Visual Acuity Measure

Table 5. Screening Visit Visual Acuity Charts

Screening Visit	Charts Used:	
VA Measure	Mesopic	Photopic
Manifest Refraction Near	23213-1 Front	23213-1 Back
Manifest Refraction Distance	23214-1 Front	23214-1 Back
CDVA	23214-2 Front	23214-2 Back
DCNVA (Repeated 3x for OU)	23213-2 Front 23213-2 Back 23213-3 Front	23213-3 Back
Cycloplegic Refraction Distance	--	23214-1 Front

Table 6. Day 1 (Baseline), Day 7 (Visit 2), and Day 14 (Exit/Visit 3) Visual Acuity Charts

Day 1 (Baseline) Day 7 (Visit 2) Day 14 (Exit/Visit 3)	Charts Used	
VA Measure	Mesopic	Photopic
Hour 0		
CDVA	23214-1 Front	23214-1 Back
DCNVA	23213-1 Front	23213-1 Back
Hour 1		
CDVA	23214-2 Front	23214-2 Back
DCNVA	23213-2 Front	23213-2 Back
Hour 3		
CDVA	23214-3 Front	23214-3 Back
DCNVA	23213-3 Front	23213-3 Back
Hour 6		
CDVA	23214-1 Front	23214-1 Back
DCNVA	23213-4 Front	23213-4 Back
Hour 7 (1 hour after the second dose)		
CDVA	23214-2 Front	23214-2 Back
DCNVA	23213-1 Front	23213-1 Back
Hour 9 (3 hours after the second dose)		
CDVA	23214-3 Front	23214-3 Back
DCNVA	23213-2 Front	23213-2 Back

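### Eligibility criterion 10 ends birth control use at study exit, 30 days before the Section 5.2 pregnancy-avoidance period ends for a subject who completes treatment

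*Protocol*

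**What the plan says.** Three places in the protocol set a period for women of childbearing potential.

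- **Section 5.1, criterion 10 (method use).** They "must practice at least 1 protocol-specified method of birth control, that is effective from Study Day 1 through study exit".
- **Section 5.1, criterion 11 (intention and egg donation).** The woman is "not considering becoming pregnant or donating eggs during the study or for approximately 30 days after the last dose of study drug".
- **Section 5.2 (avoiding pregnancy).** They "must avoid pregnancy while taking study drug(s) and for at least 30 days after the last dose of study drug". The next bullet requires commitment to one of the listed methods and gives no end date for it. Although its heading speaks of recommendations, Section 5.2 opens by making its content mandatory.

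Section 5.2 also exempts women who cannot become pregnant: "Females do not need to use birth control during or following study drug treatment if considered of nonchildbearing potential".

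On timing, Section 4.1 schedules screening, Day 1, Day 7 and Day 14 (each of the last two ± 2 days) and nothing later. Operations Manual Section 7.4, Table 6, labels the last of these as exit: "Day 1 (Baseline), Day 7 (Visit 2), and Day 14 (Exit/Visit 3) Visual Acuity Charts". Drug is given at that visit. Section 4.1 states "On visit days, study drug will be instilled bilaterally by designated site personnel at Hour 0" and again at Hour 6, and Operations Manual Section 2.1 lists both doses for the final visit.

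**The concern.** Criterion 10 is the only text that says how long a method must be used, and its end point is exit. Section 5.2 sets a safety period that runs on for at least 30 days after dosing. A reader who takes criterion 10 at face value could conclude that a method which can simply be stopped, such as a condom, a diaphragm or a pill, is no longer needed once the Day 14 visit is over.

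The eligibility list is the working text for inclusion: "Subjects must meet all of the following criteria in order to be included in the study". Operations Manual Section 3.8 places the last planned pregnancy test at the same visit: "A urine pregnancy test will be performed at screening, Day 1, and Day 14". No later contact is scheduled at which a misreading would come to light. At stake is a clear safety instruction. Efficacy, power and type I error are not involved.

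**Working it through.** The plan gives no figure to reproduce. The check is a comparison of end dates.

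**Inputs**
- Last-dose day, *d*. For a completer this is the day of the final visit (Section 4.1; Operations Manual Section 2.1).
- Exit day, *e*: Day 14, window Day 12 to 16 (Section 4.1; Operations Manual Section 7.4, Table 6).
- Earliest end of the pregnancy-avoidance period: *d* + 30 (Section 5.2).
- End of the method-use period in criterion 10: *e*.

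**Formula**

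Shortfall = (*d* + 30) − *e* = 30 − (*e* − *d*).

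**Completer (*d* = *e*)**

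| Exit day | End under criterion 10 | Earliest end under Section 5.2 | Shortfall |
|---|---|---|---|
| 12 | Day 12 | Day 42 | 30 days |
| 14 | Day 14 | Day 44 | 30 days |
| 16 | Day 16 | Day 46 | 30 days |

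**Could the scheduled visits ever close it?** The shortfall is zero only if exit comes 30 days or more after the last dose. The longest interval on schedule is a last dose on Day 1 with exit on Day 16: *e* − *d* = 15, which leaves 30 − 15 = 15 days. So a subject who stops drug early but stays to the final visit has a smaller shortfall, never none.

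**Early withdrawal from the study.** Section 5.6 asks for a discontinuation visit, preferably within 2 weeks. If that visit is assumed to fall 0 to 14 days after the last dose, the shortfall is between 30 − 14 = 16 and 30 − 0 = 30 days. The 2 weeks is a preference, so this range is illustrative.

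**Does criterion 11 supply the missing days?** It names almost the same horizon, but what it regulates is whether the woman is considering pregnancy or egg donation. A woman can meet it without using any method after exit.

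These are differences between stated end dates. They do not measure time without contraception.

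**The case against.** The strongest reply is that the texts do not contradict each other. Section 5.2 ties the 30 days to avoiding pregnancy, and its method bullet carries no end date. Criterion 10 sets a minimum period for using a method and nowhere says that contraception may stop at exit. A woman who continues her method for 30 days satisfies both. This stands: a reader might infer a direct conflict, and the wording does not support that.

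Nor does the exemption for women of nonchildbearing potential prove that all others must use a method after treatment. Releasing one group does not fix a duration for another. It hints at what was intended and no more.

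The 30-day horizon is also hard to miss. Criterion 11 is the next line of the same list, and every criterion must be met. Criterion 10 refers to methods specified in the protocol, and these are listed directly beneath the 30-day bullet in Section 5.2. The Day 14 visit is itself an occasion to explain the period. All of this makes a misreading less likely.

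What the reply does not remove is that the one stated end date for method use is shorter than the period the protocol itself sets for avoiding pregnancy. Criterion 11 does not extend it, because it concerns intention and egg donation.

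**Conclusion.** The point holds as a wording fault of low severity. For a completer, the method-use period in criterion 10 ends 30 days before the earliest end of the Section 5.2 period. For anyone who stays to the final scheduled visit, the shortfall is at least 15 days. This rests on reading study exit as the Day 14 visit, as Table 6 of the Operations Manual labels it, and on the last dose being given at that visit. No text extends exit by a follow-up period.

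A reader might go further and infer that nothing governs pregnancy after Day 14, or that subjects were left unprotected for a month. The documents do not support either. Section 5.2 continues to bind subjects, the number of women of childbearing potential is not given, and the consent wording was not available for this review. No endpoint, sample size or analysis is touched.

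**What to change.** In criterion 10, replace the end point of study exit with at least 30 days after the last dose of study drug. Optionally, change the approximate 30 days in criterion 11 to a minimum of 30 days, so that criteria 10 and 11 and Section 5.2 all state one period. Check that the consent form says the same.

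The cost is one phrase, or two with the optional edit, plus the consent check. The small downside is that the eligibility list then states a longer contraception commitment. No visit, procedure or analysis changes.
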